7.9.3 Secondary Objectives

The secondary objectives will further characterize the performance of the DiamondTemp Ablation System. All secondary endpoints will be analyzed descriptively. Analysis of all secondary objectives will use available data with no imputations for missing data, and the percentage of missing data will be displayed for each analysis.

7.9.3.1 Secondary Objective #1

Objective

Revision 1 Page 13 of 18

To estimate the freedom from a composite of SAEs occurring within 30-days post-index ablation procedure as adjudicated by an independent CEC for relatedness to the procedure or device.

Endpoint Definition and Derivation

The SAE composite endpoint is comprised of the same types of events as defined for the primary safety endpoint but occurring within 30 days post index ablation.

Analysis Methods

This secondary endpoint will be analyzed using the Kaplan-Meier method with the log-log transformation to compute the two-sided 95% confidence interval. The components of the SAE composite endpoint will also be summarized to show the number and percentage of subjects meeting each component.

Determination of Subjects/Data for Analysis

All subjects in the mITT population will be included in the analysis.

7.9.3.2 Secondary Objective #2

Objective

To estimate the freedom from documented AF/AFL/AT episodes during the effectiveness evaluation period lasting ≥ 30 seconds in duration by ECG monitoring.

Endpoint Definition and Derivation

A subject is considered a failure for this endpoint if he/she has any documented AF/AFL/AT episode ≥ 30 seconds by ECG monitoring during the effectiveness evaluation period.

Analysis Methods

This secondary endpoint will be analyzed using the Kaplan-Meier method with the log-log transformation to compute the two-sided 95% confidence interval.

Determination of Subjects/Data for Analysis

All subjects in the mITT population will be included in the analysis.

7.9.3.3 Secondary Objective #3

Objective

To estimate the freedom from documented AF/AFL/AT episodes during the effectiveness evaluation period in the absence of class I and III anti-arrhythmic drug therapy.

Endpoint Definition and Derivation

A subject is considered a failure for this endpoint if he/she has any documented AF/AFL/AT episode and/or uses any class I/III AAD during the effectiveness evaluation period.

Revision 1 Page 14 of 18

Analysis Methods

This secondary endpoint will be analyzed using the Kaplan-Meier method with the log-log transformation to compute the two-sided 95% confidence interval.

Determination of Subjects/Data for Analysis

All subjects in the mITT population will be included in the analysis.

7.9.3.4 Secondary Objective #4

Objective

To estimate the rate of acute procedural success.

Endpoint Definition and Derivation

An acute procedural success is defined as confirmation of electrical isolation of PVs at least 20 minutes following the last ablation around the respective PV.

Analysis Methods

This secondary endpoint will be analyzed using the Binomial method and an exact 95% confidence interval will be constructed.

Determination of Subjects/Data for Analysis

All subjects in the mITT population will be included in the analysis. The analysis will be based on index ablation procedures only.

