2.2 Table of Definitions

Term	Definition
ACT	ACT is a test that is used to monitor the effectiveness of the administration of Heparin through measuring activated clotting time (ACT)
Asymptomatic AF, AT or AFL	Also known as silent AF or silent atrial tachycardia (e.g. AT, AFL). Defined as an opportune diagnosis of AF, AT, and/or AFL with electrocardiographic data; specifically, subject's event monitor, 24 hr. Holter monitor or 12 lead ECG at clinic visit.

DIAMOND-AF II Clinical Investigation Plan

Version H

Page 9 of 111

Medtronic
Form

Atrioesophageal fistula	Creation of direct communication between the left atrium and esophagus as documented by esophageal erosion combined with evidence of a fistulous connection to the atrium (e.g. air emboli, an embolic event or direct observation at the time of surgical repair). A CT or MRI scan is recommended to document event.																												
Attempt Subject	Refers to a subject who has been enrolled and has treatment catheter introduced but does not receive an ablation with the catheter per protocol.																												
Blanking Period	The ~ 90-day period between ablation procedure and the 3-month follow-up visit. During the blanking period, a repeat ablation can be performed with the same treatment catheter subject originally was treated with. Subjects can be prescribed antiarrhythmic drugs as determined necessary by the Investigator during blanking period.																												
Bleeding complication	Major bleed that requires a transfusion or results in a $\geq 20\%$ fall in hematocrit.																												
Cardiac tamponade / perforation	Significant pericardial effusion with hemodynamic compromise that requires elective or urgent pericardiocentesis or results in a 1-cm or more pericardial effusion as documented by echocardiography.																												
CHA ₂ DS ₂ -VASc score	Clinical prediction rules for estimating stroke risk in patients with non-rheumatic AF. The rule gives a better risk stratification of low-risk patients than CHADS2 score by inclusion of additional stroke risk modifier risk factors.																												

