If at any time during the ablation procedure the Investigator is unable to continue the ablation with the investigational catheter (other than when ablating an RA flutter line), the Investigator may consider the case a procedural failure and complete the case with a device determined best for the subject. The point at which failure was determined as well as the rationale must be documented.

After removal from the subject, the investigational catheter should be inspected, and if any abnormalities such as char or coagulum formation are noted on the catheter, it must be documented. All adverse experiences with the investigational device during the ablation procedure must be promptly reported to the Sponsor and documented on the CRF.

Post-Procedure Anticoagulation

Investigators may use protamine to reverse the intravenous heparin used during the procedure.

- Subjects must be anticoagulated for a minimum of 60 days post index ablation procedure. It is up to the Investigator's discretion which drug is best suited for the subject.
- If anticoagulation was discontinued prior to and during the ablation procedure, anticoagulation should be resumed within 24 hours post-procedure to achieve a therapeutic anticoagulation level.
- It is recommended that Investigators follow the anticoagulation guidelines set forth in the 2017 HRS Expert Consensus Statement on Catheter and Surgical Ablation of AF^[10], regardless of the apparent success or failure of the AF ablation procedure.
- Additionally, the Investigator's decision regarding continuation of systemic anticoagulation more than 60 days post ablation should be based on the subject's stroke risk profile (CHA₂DS₂-VASc score ≥ 2 in men and ≥ 3 in women, prior stroke or TIA and/or age ≥ 75 years) and not on the perceived success or failure of the ablation procedure.

Post-Procedure AADs

- If AADs are restarted following the ablation procedure, it is recommended to maintain subjects on a drug regimen for a duration of 2 to 4 weeks to address symptoms or early recurrences of AF, AFL or AT during the post-ablation healing and stabilization phase.
- If AADs are restarted for clinical reasons during the blanking period but not later than the 3-month follow-up visit, it is recommended that subjects are maintained under the same AAD regimen throughout the effectiveness period (12-month follow-up). During the effectiveness evaluation period, physicians may discontinue an AAD, but may not add a new class or escalate an AAD.

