14.5.4 Secondary Objective #4

Objective

To estimate the rate of acute procedural success.

Endpoint Definition and derivation

An acute procedural success is defined as confirmation of electrical isolation of PVs at least 20 minutes following the last ablation around the respective PV.

Analysis Methods

This secondary endpoint will be analyzed using the Binomial method.

Determination of Subjects/Data for Analysis

All subjects in the mITT population will be included in the analysis. The analysis will be based on index ablation procedures only.

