7.9.2 Primary Effectiveness Objective

Primary Effectiveness Objective

To demonstrate that the primary effectiveness rate associated with the DiamondTemp ablation system is higher than the pre-specified Objective Performance Criterion (OPC).

Hypothesis

Revision 1

Page 11 of 18

 H_0 : $P \leq P_0$

 $H_1: P > P_0$

where $P_0 = 40\%$ (Effectiveness OPC), and higher effectiveness rates are better.

Endpoint Definition and Derivation

The primary effectiveness endpoint is defined as freedom from documented Atrial Fibrillation (AF), Atrial Flutter* (AFL) and Atrial Tachycardia (AT) episodes following the blanking period (3-month followup post-ablation procedure) through the end of the effectiveness evaluation period (12-month followup post-ablation procedure).

An effectiveness failure is defined by any of the following events:

- Inability to electrically isolate all accessible targeted pulmonary veins during the ablation procedure.
- Documented episodes of AF, AFL or AT lasting ≥ 30 seconds in duration as evidenced by electrocardiographic data during the effectiveness evaluation period.
- DC cardioversion for AF, AFL or AT during the effectiveness evaluation period.
- A repeat ablation procedure to treat AF, AFL or AT during the effectiveness evaluation period.
- Use of a new or previously failed anti-arrhythmic drug (AAD) at a dose greater than the highest ineffective dose for AF during the effectiveness evaluation period.
- Use of a non-study device for ablation of any AF targets during the index or repeat ablation procedure during the blanking period.
- More than one (1) repeat ablation procedure during the blanking period.

The blanking period for a subject starts on the date of the index ablation procedure (day 0) and ends on day 90 post index ablation.

The effectiveness evaluation period for a subject starts on day 91 post index ablation and ends on the study exit date or day 410 post index ablation (i.e., close of the 12-month visit window), whichever is earlier.

If a primary effectiveness failure event occurs post day 365 and within the effectiveness evaluation period, the date of the event will be set to day 365 so that these events will be accounted for in the 12month Kaplan-Meier estimate of the primary effectiveness endpoint.

Performance Requirements

The null hypothesis will be rejected if the one-sided 97.5% lower confidence bound of the primary effectiveness rate is greater than 40%.

[figure not shown]

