7.9.3.5 Secondary Objective #5

Objective

To estimate the rate of single procedure success with freedom from AF/AFL/AT recurrence.

Endpoint Definition and Derivation

A subject is considered a single procedure success if he/she is treated with one single ablation procedure during study participation and free from documented AF/AFL/AT episode at 12 months post index ablation.

Analysis Methods

This secondary endpoint will be analyzed using the Kaplan-Meier method with the log-log transformation to compute the two-sided 95% confidence interval.

Determination of Subjects/Data for Analysis

All subjects in the mITT population will be included in the analysis.

Revision 1 Page 15 of 18

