7.9.3.6 Secondary Objective #6

Objective

To estimate the rate of single procedure success with freedom from all primary effectiveness failure criteria.

Endpoint Definition and Derivation

A subject is considered a single procedure success if he/she is treated with one single ablation procedure during study participation and free from all primary effectiveness failure criteria at 12 months post index ablation.

Analysis Methods

This secondary endpoint will be analyzed using the Kaplan-Meier method with the log-log transformation to compute the two-sided 95% confidence interval.

Determination of Subjects/Data for Analysis

All subjects in the mITT population will be included in the analysis.

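### Acute procedural success (Secondary #4) does not require the study catheter, so an index case rescued with another catheter can count as a DiamondTemp success

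*SAP*

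**What the plan says.** The SAP (7.9.3.4) counts an acute procedural success as "confirmation of electrical isolation of PVs at least 20 minutes following the last ablation around the respective PV". Protocol 14.5.4 uses the same definition. The analysis set is mITT, and the SAP adds: "The analysis will be based on index ablation procedures only". The method is binomial with an exact 95% confidence interval.

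Protocol 10.6.2 covers the case in which the investigator cannot go on with the investigational catheter, other than for a right-atrial flutter line. It says "the Investigator may consider the case a procedural failure and complete the case with a device determined best for the subject", and requires the point of failure and the reason to be documented.

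mITT (SAP 7.1.3) needs consent, eligibility and insertion of the catheter into the vasculature. Treatment with a non-study catheter removes a subject only from the Per Protocol set, and that set is used only for the primary objectives. The Protocol glossary (2.2) also defines an Attempt Subject, who "has treatment catheter introduced but does not receive an ablation with the catheter per protocol". An eligible Attempt Subject is in mITT.

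The primary effectiveness endpoint (SAP 7.9.2) lists as a failure: "Use of a non-study device for ablation of any AF targets during the index or repeat ablation procedure during the blanking period". Secondary #6 takes this over, because it requires the subject to be "free from all primary effectiveness failure criteria at 12 months post index ablation". Secondary #4 does not.

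**The concern.** SAP 7.9.3 presents the secondary objectives as describing how the DiamondTemp system performs. Acute isolation is the most direct of these measures: whether the veins were isolated at the end of the index case. As defined, it asks whether they were isolated by any catheter used in that session. The two questions differ only in cases where the study catheter could not finish the job, and there the definition credits DiamondTemp with the result of its replacement.

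At stake is a descriptive performance figure that is likely to be quoted on its own. Acute isolation rates tend to lie near the ceiling: the first-in-human study in Protocol 4.1.7 reports 100%, although in paroxysmal AF and after leaving out two enrolled subjects in whom isolation with the study device was not attempted. Near the ceiling, how a handful of rescued cases is scored changes both the estimate and its lower bound.

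**Working it through.** **1. Does the definition as written admit a rescued case?**

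| Step | Source | Result for a subject rescued at the index |
|---|---|---|
| Switch of catheter foreseen in the same session | Protocol 10.6.2 | Yes |
| Subject in mITT | SAP 7.1.3 | Yes, if eligible; insertion is enough |
| Session in scope for #4 | SAP 7.9.3.4 | Yes, it is the index procedure |
| Device condition in #4 | SAP 7.9.3.4, Protocol 14.5.4 | None |
| Success on #4 | SAP 7.9.3.4 | Yes, if isolation is confirmed after the 20-minute wait |
| Primary effectiveness | SAP 7.9.2 | Failure, if an AF target was ablated with the other device |
| Per Protocol analysis of #4 | SAP 7.1.3, 7.9 | None planned |

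The discretionary procedural-failure label in 10.6.2 is not used in either statement of the #4 definition. The same path holds for an eligible Attempt Subject whose veins are all isolated with another catheter.

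**2. Size**

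The documents give no target, expected rate or rescue rate for #4, so there is no plan figure to reproduce. The following is an illustration.

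Inputs: N = 274, the effectiveness sample size in SAP 6, used here as a stand-in for the mITT count. Assumed: every subject leaves the laboratory with isolation confirmed, and r of them were rescued with a non-study catheter.

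- Rate as written: 274/274, whatever r is.
- Rate with a study-catheter requirement: (274 − r)/274.
- Overstatement: r/274.
- Assumed range of 1–5%: 0.01 × 274 = 2.7 and 0.05 × 274 = 13.7, so about 3–14 subjects.

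With x successes out of n, the exact (Clopper-Pearson) 95% limits are the 2.5% quantile of Beta(x, n − x + 1) and the 97.5% quantile of Beta(x + 1, n − x). When x = n, the lower limit is 0.025^(1/n). For n = 274 this is 0.025^(1/274) = 0.9866.

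| Rescued, r | r/274 | As written (exact 95% CI) | Study catheter required (exact 95% CI) |
|---|---|---|---|
| 0 | 0% | 100% (98.7–100) | 100% (98.7–100) |
| 3 | 1.1% | 100% (98.7–100) | 271/274 = 98.9% (96.8–99.8) |
| 6 | 2.2% | 100% (98.7–100) | 268/274 = 97.8% (95.3–99.2) |
| 8 | 2.9% | 100% (98.7–100) | 266/274 = 97.1% (94.3–98.7) |
| 14 | 5.1% | 100% (98.7–100) | 260/274 = 94.9% (91.6–97.2) |

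The difference is one-for-one in the number rescued with confirmed isolation and cannot be negative.

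**The case against.** The strongest reply is that nothing rests on this endpoint. The secondary objectives are descriptive and untested (SAP 7.5), study success depends only on the two primary objectives, and primary effectiveness already counts non-study-device use as failure. That is correct, and it limits the weight of the point.

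A second reply is that the information is already disclosed. SAP 7.9.2 asks for the number and percentage of subjects meeting each primary failure component, and non-study-device use is one. This partly stands: a reader could put an upper bound on the index rescues. But that component pools the index procedure with repeat procedures in the blanking period, and it does not show how many rescued subjects had confirmed isolation. It bounds the correction to #4 without giving it.

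Third, the rescue rate is unknown. That is so; the sizes above are conditional on the assumed range.

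Several stronger readings are tempting, but the documents do not support them:

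- A reader might infer that 10.6.2 classes every rescued case as a procedural failure, so that #4 turns a defined failure into a success. The text only permits the investigator to regard it as one. What follows is that 10.6.2 and the endpoint definition need to be reconciled.
- A reader might infer that the report would contradict itself, with one subject both a primary failure and an acute success. Two endpoints with different definitions can differ for one subject without contradiction. Nor does SAP 7.9.2 give a failure date for the index criteria, so a day-0 failure cannot be read from it.
- A reader might extend the point to #2, #3 and #5. These are recurrence endpoints (#3 adds drug use). #5, for instance, asks whether a subject was "treated with one single ablation procedure during study participation and free from documented AF/AFL/AT episode at 12 months post index ablation". Recurrence in all attempted subjects is a legitimate descriptive quantity, and versions with a device criterion are already planned in the primary endpoint and #6. Secondary #4 has no such counterpart.
- A reader might infer that rescue means automatic success. It does not: isolation must still be confirmed after the wait.

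**Conclusion.** The point holds for Secondary #4 only. As defined, acute procedural success credits DiamondTemp with any isolation confirmed at the index procedure, including isolation achieved by a catheter that replaced it, and no planned analysis of #4 applies a device criterion. The bias is upward only and equals the proportion of mITT subjects rescued at the index with confirmed isolation. If that is 1–5% of 274, the overstatement is about 3–14 subjects, or 1.1 to 5.1 percentage points. This rests on the assumed rescue rate, on 274 as the denominator, and, for the tabulated rates and intervals, on all subjects leaving with isolated veins. If no case is rescued, the effect is nil. Neither primary objective, Secondary #6 nor the study success decision is affected. It is an inexpensive correction to a descriptive endpoint.

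**What to change.** In SAP 7.9.3.4, add that acute procedural success requires isolation of all accessible targeted PVs with the study catheter, and that use of a non-study device for any AF target at the index procedure is scored as failure. Exempt a right-atrial flutter line, consistent with Protocol 10.6.2. Carry the same wording into Protocol 14.5.4 at the next amendment. As a supplement, report the number of index cases completed with a non-study catheter and the isolation rate by any catheter, so that both quantities are visible.

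Leave #2, #3 and #5 as they are. The change concerns scoring only and does not touch what the investigator may do under 10.6.2.

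Cost: one sentence in the SAP, the matching Protocol edit when it is next amended, and two extra lines of output. Non-study-device use must already be captured for the primary endpoint, so no new data are needed. The downside is that the reported acute success rate may fall slightly.

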7.9.3.5 Secondary Objective #5

Objective

To estimate the rate of single procedure success with freedom from AF/AFL/AT recurrence.

Endpoint Definition and Derivation

A subject is considered a single procedure success if he/she is treated with one single ablation procedure during study participation and free from documented AF/AFL/AT episode at 12 months post index ablation.

Analysis Methods

This secondary endpoint will be analyzed using the Kaplan-Meier method with the log-log transformation to compute the two-sided 95% confidence interval.

Determination of Subjects/Data for Analysis

All subjects in the mITT population will be included in the analysis.

Revision 1 Page 15 of 18

7.9.3.6 Secondary Objective #6

Objective

To estimate the rate of single procedure success with freedom from all primary effectiveness failure criteria.

Endpoint Definition and Derivation

A subject is considered a single procedure success if he/she is treated with one single ablation procedure during study participation and free from all primary effectiveness failure criteria at 12 months post index ablation.

Analysis Methods

This secondary endpoint will be analyzed using the Kaplan-Meier method with the log-log transformation to compute the two-sided 95% confidence interval.

Determination of Subjects/Data for Analysis

All subjects in the mITT population will be included in the analysis.

7.9.3.7 Secondary Objective #7

Objective

To evaluate changes in QOL using the AFEQT Questionnaire.

Endpoint Definition and Derivation

Subject's QOL is measured using the AFEQT Questionnaire at baseline, 6-month visit and 12-month visit. The QOL change from baseline to 6 months, as well as change from baseline to 12 months will be calculated for each subject.

Analysis Methods

This secondary endpoint will be analyzed using descriptive statistics.

Determination of Subjects/Data for Analysis

All subjects in the mITT population will be included in the analysis.

7.9.3.8 Secondary Objective #8

[figure not shown]
Objective

To evaluate neurological changes measured using the NIH stroke scale.

Endpoint Definition and Derivation

Subject's neurological function is measured using the NIH stroke scale at baseline, pre-discharge visit and 12-month visit. The neurological change from baseline to pre-discharge, as well as change from baseline to 12 months will be calculated for each subject.

Revision 1 Page 16 of 18

Analysis Methods

This secondary endpoint will be analyzed using descriptive statistics.

Determination of Subjects/Data for Analysis

All subjects in the mITT population will be included in the analysis.

